Subjects for whom one aDBS mode is unacceptable as compared to cDBS (using the aDBS GIC) or for whom only one mode could be acceptably configured will not be randomized and will complete one aDBS evaluation visit in the aDBS mode that was acceptable to the subject.

In order to blind the subject to the aDBS mode assigned, the clinician will set the group name of the aDBS mode being evaluated during each period to "aDBS," and the group name of the mode not being evaluated to "Do not use" on the Clinician Programmer. These group names will be displayed on the Patient Programmer.

Medtronic Business Restricted

If neither aDBS mode is acceptable to the subject, the subject will be exited from the study following the process in [Section 9.19](#). No further study-related procedures will be completed, and the subject will be followed according to the center's standard procedures.

If randomization is conducted as a separate visit, the programming session, with BrainSense data included in the JSON session data report, will be uploaded to Medtronic via CDU.

The subject will be instructed on the use of the PKG Watch and PD Home Diary in the aDBS Evaluation Phase.

9.10. aDBS Evaluation Phase

This phase consists of up to two treatment periods; one per acceptable aDBS mode. After each treatment period, there is an aDBS evaluation visit. The subject's PD medications will remain stable from enrollment through the end of the aDBS Evaluation Phase, unless changes are clinically necessary.

During the aDBS Evaluation Phase, the subject may return to the study center for further aDBS adjustment in each randomized aDBS mode. All adjustments must be completed at least 14 days prior to the evaluation visit for that mode. Any adjustments will be recorded as unscheduled visits. Any adjustments during the 14 days prior to the evaluation visit will be considered a protocol deviation.

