Next, the clinician will program the subject to the other assigned aDBS mode and label that group “aDBS.” The group for the aDBS mode the subject just completed evaluation of will be re-labeled “Do not use” on the Patient Programmer.

The subject should be reminded that they will receive the PKG Watch prior to the aDBS Evaluation Visit 2 and will put on and activate the PKG Watch upon receipt. The subject will wear the PKG Watch for at least 6 consecutive days in the 14 days prior to the scheduled aDBS Evaluation Visit 2. After the recording, the subject will return the PKG Watch in the pre-paid mailer or bring it to the site for return at the visit. The subject will also be reminded that they will be provided with the PD Home Diary in advance of the visit and will complete it for at least 3 consecutive days in the 14 days prior to the next aDBS Evaluation Visit.

If only one aDBS mode is being evaluated, the subject will continue into the Long-term Follow-up phase and skip aDBS Evaluation Visit 2.

9.10.2. Evaluation Visit 2

If two aDBS modes are being assessed

30-45 days after Evaluation visit 1

Medtronic Business Restricted

The subject will arrive for the visit on their normal PD medications and on aDBS.

The clinician will confirm the subject is in the assigned mode for this visit. If the subject is not in aDBS, the clinician will program the subject to the assigned aDBS mode and all On stim assessments will be performed in the assigned mode. If the subject completed the evaluation period in the incorrect aDBS mode, all On stim assessments will be performed in the incorrect aDBS mode.

The following data will be collected:

- PDQ-39
- EQ-5D-5L
- C-SSRS
- MDS-UPDRS I (Part A) – trained rater
- MDS-UPDRS Patient Questionnaire (Part IB and II) (best condition)
- MDS-UPDRS Patient Questionnaire (Part IB and II) (worst condition)
- MDS-UPDRS III (On stim (aDBS)/On med) – trained rater
- MDS-UPDRS IV – trained rater
- VHI (worst condition)
- VHI (best condition)
- PDSS-2
- Patient preference questionnaire
- Collect PD Home Diary and review for completeness
- Concomitant medications
- Patient and physician preferred aDBS mode and reason for selecting preferred mode (at end of visit)
- Collect PKG Watch or confirm it was returned via mail
- Adverse Event and device deficiency assessment

At the end of the visit, the programming session, with BrainSense data included in the JSON session data report, will be uploaded to Medtronic via CDU.

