Following the final aDBS visit, the clinician will program the subject to the chosen DBS mode (clinician & patient preference) for the long-term follow-up phase and record the reason for selecting that mode.

If the chosen DBS mode is cDBS, the subject will be exited from the study following the process in [Section 9.19](#). No further study-related procedures will be completed, and the subject will be followed according to the center's standard procedures.

The subject should be reminded that they will receive the PKG Watch prior to the next visit and will put on and activate the PKG Watch upon receipt. The subject will wear the PKG Watch on the most affected side for at least 6 consecutive days in the 14 days prior to the scheduled visit.

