2.0	
Aligned with Version 3.0 of CIP, including:
 
 Added the Directional Stimulation cohort Added TEED calculations for subjects implanted with the SenSight system Added poolability analyses of a lead type effect (legacy Models 3387 and 3389 compared to SenSight Models B33005 and B33015) for the primary and secondary objectives and safety assessment Added supportive analyses of the Directional Stimulation Cohort for the primary and secondary objectives and safety assessment Updated the Patient Preference and Patient Satisfaction analyses and screenshots 
Other updates include:
 
 Specified that PD Home Diary complete diary periods collected anytime during cDBS will be used for analysis Added examples of coding that could be used for multiple imputation analyses, tests of a period or carryover effect, and poolability tests of the primary and secondary objectives and safety assessment Defined the safety evaluation populations 	[REDACTED]
3.0	
 Updated the document using the current SAP template Added SAP version date to cover page per ClinicalTrials.gov requirements Editorial updates for clarifications 	[REDACTED]
4.0	
Aligned with Version 5.0 of CIP, including:
 
 Allowed for impedance values from aDBS Setup Visit to be used for analysis in case they were not collected at cDBS Baseline or aDBS Evaluation Phase Added a subgroup analysis of outcomes during Evaluation Phase by the mode selected for the Long-term Follow-up 	[REDACTED]

2. List of Abbreviations and Definitions of Terms

Abbreviation	Definition
AC	All-Consented
AE	Adverse Event
aDBS	Adaptive Deep Brain Stimulation
AR	All-Randomized
AT	As-Treated
Best condition	The time period when PD subjects are receiving relief from their Parkinson's disease symptoms, also known as "on" time or "on" period
BKS	Bradykinesia Score
cDBS	Continuous Deep Brain Stimulation
CC	Complete-Case
CIP	Clinical Investigation Plan
CONSORT	Consolidated Standards of Reporting Trials
CRF	Case Report Form
DBS	Deep Brain Stimulation
DS	Directional Stimulation Cohort comprised of study subjects with the SenSight™ Directional Lead programmed to directional stimulation
DKS	Dyskinesia Score
EQ-5D-5L	Five-dimensional five-level generic measure designed to measure, compare and value health status across disease areas; developed by the EuroQol Group.

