4.4 Additional objectives

To characterize aDBS during the Evaluation Phase as compared to cDBS (Primary Cohort):

- Voice Handicap Index (VHI): “best” and “worst” conditions
- Movement Disorder Society Unified Parkinson’s Disease Rating Scale (MDS-UPDRS) Part III subscore (On stim/On med) of tremor, rigidity, and bradykinesia questions where a side can be determined: 3.3 b, c, d, e (rigidity), 3.4 a, b (finger taps/bradykinesia), 3.15 a, b (postural tremor of hands), 3.16 a, b (kinetic tremor of hands), and 3.17 a, b, c, d (rest tremor amplitude)
- MDS-UPDRS III (On stim/On med)
- MDS-UPDRS II: “best” and “worst” conditions
- MDS-UPDRS III speech question (On stim/On med) q 3.1
- MDS-UPDRS IV
- European Quality of Life – 5 Dimensions, version 5L (EQ-5D-5L)
- Parkinson’s Disease Sleep Scale 2 (PDSS-2)
- Data collected from wearable (for example: % of wear time tremor was detected, Dyskinesia Score [DKS], Bradykinesia Score [BKS], Fluctuation and Dyskinesia Score [FDS])

- Parkinson's Disease Questionnaire (PDQ)-39 Summary Index (SI) and subscores: mobility, activities of daily living, emotional well-being, stigma, social support, cognition, communication, bodily discomfort
- PDQ-39 speech questions 34 and 35
- % of subjects with at least 25% increase in projected battery longevity as compared with cDBS
- Parkinson's Disease (PD) Home Diary: "On" time without troublesome dyskinesia, "On" time without dyskinesia, "On" time with non-troublesome dyskinesia, "On" time with troublesome dyskinesia, "Off" time, and Asleep time.
- Patient preference of aDBS vs cDBS (as assessed by a Medtronic-developed patient preference questionnaire)
- Patient satisfaction with aDBS (as assessed by a Medtronic-developed patient satisfaction questionnaire)
- Device data from JavaScript Object Notation (JSON) file, including BrainSense data

Subgroup analyses (from the entire study population):

- For those with dyskinesia at least 25% of time: Wearable data
- For those with speech side effects: VHI
- For those with mixed programming (aDBS and cDBS): MDS-UPDRS III by side
- For those who use event markers in long-term follow-up: characterize subject population and satisfaction with use of event markers
- For those who finished the aDBS Evaluation Phase: one aDBS mode will be selected per subject based on subject preference or programming availability at the end of the aDBS Evaluation Phase. The aDBS Evaluation Phase results may be characterized based on the selected mode.

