7.9.3 Additional Objectives

To characterize each aDBS mode as compared to cDBS, the additional objectives described in sections 7.9.3.1 through 7.9.3.9 will be evaluated separately for each aDBS mode. The additional objectives in section 7.9.3.10 through 7.9.3.11 will characterize each aDBS mode, separately, without comparisons to cDBS. Additional objectives will be characterized for the CC unless otherwise specified, and the subgroup analyses described in section 4.4 will be performed on the CC analysis set and DSAT combined. Relevant references for additional objectives can be found in the study CIP.

Summary statistics may be presented for continuous measures (e.g., N, means, medians, standard deviations, minimums and maximums) and categorical measures (e.g., N, percentage, frequency distributions) with 95% confidence intervals as appropriate. If performed, missing data imputations will be conducted as specified within the respective sections. No adjustment will be made for multiple testing as no hypothesis testing will be conducted for the additional objectives.

To characterize aDBS as compared to cDBS for the objectives in sections 7.9.3.1 through 7.9.3.7, summary statistics will be provided in each aDBS mode and in cDBS along with the difference in aDBS and cDBS for continuous objectives. The difference will be calculated as follows for outcomes in which higher values are better:

$$\Delta_{\text{aDBS dual threshold mode}} = \theta_{\text{aDBS dual threshold mode}} - \theta_{\text{cDBS}}$$

and

$$\Delta_{\text{aDBS single threshold mode}} = \theta_{\text{aDBS single threshold mode}} - \theta_{\text{cDBS}}$$

And as follows for outcomes in which lower values are better:

$$\Delta_{\text{aDBS dual threshold mode}} = \theta_{\text{cDBS}} - \theta_{\text{aDBS dual threshold mode}}$$

and

$$\Delta_{\text{aDBS single threshold mode}} = \theta_{\text{cDBS}} - \theta_{\text{aDBS single threshold mode}}$$

Where Δ is the mean within-patient change in the objective between the respective aDBS mode and cDBS mode.

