7.9.3.8 Patient Preference

Patient preference for aDBS vs. cDBS and Single vs. Dual Threshold aDBS modes (if both were evaluated) will be assessed by a Medtronic-developed questionnaire.

The questionnaire has three parts, the first assessing subject preference for aDBS as compared with the cDBS therapy they received before starting the study, to which subjects can reply that they strongly

prefer aDBS, somewhat prefer aDBS, no preference between aDBS and cDBS, somewhat prefer cDBS, or strongly prefer cDBS. The specific questions asked in part I are displayed in Figure 7-1.

The second part assesses subject blinding. Subjects report which aDBS mode they believe they received in the relevant period, why they believe that to be true, and how certain they are about their assessment. The specific questions are displayed in Figure 7-2.

The third part assesses subject preference for aDBS mode among subjects receiving therapy with both aDBS modes, to which subjects can reply that they prefer the first aDBS mode received, the second aDBS mode received, no preference, or do not know. The questions asked in part III are displayed in Figure 7-3.

Figure 7-1. Evaluation of aDBS therapy as compared to DBS therapy received prior to study start

Section I: Evaluation of the DBS Therapy Received Over the Past 14 Days

Instructions: We are interested in your evaluation of the deep brain stimulation (DBS) therapy you received over the past 14 days and would like you to compare it to the DBS therapy you were receiving before you joined the research study. Think about how effective the therapy was on your disease-related symptoms (examples: shaking, slowness, stiffness) and any side effects (examples: trouble swallowing, change in mood, tingling) caused by the DBS therapy you are receiving. For each question, please place a single check mark next to the response you feel best represents your experience and preferences.

Overall, do you prefer the DBS therapy you received during the past 14 days or the DBS therapy you were receiving prior to joining the research study

- Strongly prefer the DBS therapy received during the last 14 days.
- Somewhat prefer the DBS therapy received during the last 14 days.
- No preference between the two.
- Somewhat prefer the DBS therapy I was receiving prior to joining the research study.
- Strongly prefer the DBS therapy I was receiving prior to joining the research study.

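### The optional selected-mode summary picks each subject's aDBS mode after both periods and then summarises those same periods, so it tends to favour aDBS when preference tracks outcome (minor)

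*SAP*

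**What the plan says.** The rule is in SAP 4.4, in the list of subgroup analyses, and also in the protocol synopsis and protocol 4.1.4. It covers every subject who completes that part of the trial and sets the choice this way: "one aDBS mode will be selected per subject based on subject preference or programming availability at the end of the aDBS Evaluation Phase". A further sentence then allows the summary: "The aDBS Evaluation Phase results may be characterized based on the selected mode".

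Other relevant text:

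- **Timing.** Protocol 9.10.2 lists this item at Evaluation Visit 2: "Patient and physician preferred aDBS mode and reason for selecting preferred mode (at end of visit"). By then the diary, MDS-UPDRS, VHI, PDQ-39 and wearable data from both periods have been collected.
- **One-mode subjects.** Under protocol 9.9.3 a subject with a single acceptable mode "will complete one aDBS evaluation visit in the aDBS mode that was acceptable to the subject", so there is no choice between modes.
- **cDBS choosers.** Protocol 9.10.2: "If the chosen DBS mode is cDBS, the subject will be exited from the study".
- **Version history.** The SAP 4.0 entry describes the change as follows: "Added a subgroup analysis of outcomes during Evaluation Phase by the mode selected for the Long-term Follow-up".
- **Preference answers.** SAP 7.9.3.8 describes a mode-preference part "to which subjects can reply that they prefer the first aDBS mode received, the second aDBS mode received, no preference, or do not know".
- **Analysis set and status.** SAP 7.9.3 says "the subgroup analyses described in section 4.4 will be performed on the CC analysis set and DSAT combined". It plans no hypothesis tests for the additional objectives, and allows 95% confidence intervals where appropriate.

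**The concern.** For a two-mode subject, the choice of mode and the results reported for it come from the same two periods. Preference is also meant to reflect how the subject did: the questionnaire shown in SAP Figure 7-3 asks subjects to think about symptom control and side effects before naming a mode. A period that went well by chance is then more likely to be selected, and its chance component enters the summary. The cDBS Baseline has no matching selection. A difference between the two, computed as in SAP 7.9.3, can be positive when neither mode differs from cDBS.

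At stake is a single aDBS-versus-cDBS figure per subject, possibly with a confidence interval. It is easy to quote, and nothing in the text corrects it for the selection or requires a caution. The undefined place of subjects who prefer to return to cDBS matters for the same reason: leaving them out would remove subjects likely to have done less well on aDBS.

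**Working it through.** The documents give no figure for this analysis, so there is none to reproduce. The question is how large the lean could be.

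**Inputs.** From the documents: selection at the end of the phase, the same phase summarised, and one cDBS Baseline. Assumed, because the documents give no values:

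- f, the share of subjects with both modes;
- rho, the correlation between a subject's two changes from cDBS (both changes use the same Baseline value, so a positive correlation is expected);
- c, the correlation between preference and the observed difference between the modes;
- no true change from cDBS, no true mode difference, and normal changes with SD 1.

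**Formula.** Call the two changes A and B, and D = A − B. The SD of D is sqrt(2(1 − rho)). The selected result is the average of A and B, plus D/2 if A is chosen or minus D/2 if B is chosen. The average has mean 0. The expected value of the second part is (1/2) × c × sqrt(2(1 − rho)) × sqrt(2/pi) = c × sqrt((1 − rho)/pi). One-mode subjects contribute 0, so

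inflation = f × c × sqrt((1 − rho)/pi), in SD of change.

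**Numbers.** At rho = 0.5, sqrt(0.5/3.1416) = 0.399.

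| f | rho | c | inflation (SD) |
|---|---|---|---|
| 1 | 0.5 | 0 | 0 |
| 1 | 0.5 | 0.3 | 0.12 |
| 1 | 0.5 | 0.5 | 0.20 |
| 1 | 0.5 | 1 | 0.40 |
| 1 | 0.3 | 0.5 | 0.24 |
| 1 | 0.8 | 0.5 | 0.13 |
| 0.5 | 0.5 | 0.3 | 0.06 |
| 0.5 | 0.5 | 0.5 | 0.10 |
| 0.5 | 0.5 | 1 | 0.20 |

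A simulation of 1,000,000 subjects per setting agrees (for example 0.118, 0.200 and 0.399 at f = 1, rho = 0.5 and c = 0.3, 0.5 and 1).

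**On the scale of the primary threshold.** The share at or above −1 SD is 84.1% without selection and 88.9% at f = 1, rho = 0.5, c = 0.5. This is illustration only: the SAP does not say that the threshold is applied to the selected-mode summary.

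**If cDBS choosers were left out.** Take that same setting and drop the lowest 5% or 10% on an index correlated 0.5 with the selected-mode change. The inflation rises from 0.20 to 0.25 or 0.30 SD, and the share to 90.6% or 91.6%. The 5% and 10% are assumptions.

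**Are they left out?** Two readings are possible:

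- The rule in SAP 4.4 covers every finisher and gives each one an aDBS mode. A cDBS chooser exits only after the final evaluation visit, and the preferred aDBS mode is a separate Visit 2 item with no exception for such subjects. On this reading they stay in.
- The version-history entry ties the grouping to the mode selected for long-term follow-up. A subject exited for choosing cDBS has no such mode. On this reading they drop out.

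Nothing settles which is meant. There is likewise no rule for subjects who state no preference or do not know, or for disagreement between patient and physician.

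**The case against.** The strongest reply is that little depends on this analysis. It is optional, descriptive and untested. The primary and secondary hypotheses are tested for each mode separately, or on pooled first-period data under SAP 7.2.1. The additional objectives are already planned separately for each mode, so unselected results will be available, and preference for cDBS and attrition are reported elsewhere. All of this stands, and it makes the point minor. It does not remove the point: the selected-mode figure can still be reported with no unselected counterpart for the same subjects.

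Four stronger readings might be inferred, and the documents do not support them:

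- **That subjects who chose cDBS have no selected mode and are excluded.** Only the version-history wording points that way. The operative rule and the Visit 2 data item allow every finisher a mode.
- **That the summary necessarily overstates benefit.** The inflation is zero if preference is unrelated to the outcome, and mode choice adds none in one-mode subjects. Part of any gain is real if subjects truly differ in which mode suits them. The 0.40 SD case needs perfect selection, and one overall preference cannot pick the better period on every outcome at once.
- **That this is the only analysis with one aDBS result per subject, and so the headline.** The conditional pooled first-period analysis also gives one, without selection. No text gives the selected-mode summary a headline role.
- **That Visits 3 to 6 would give a clean replacement.** cDBS choosers are absent there, and protocol 9.11 lets investigators switch modes.

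**Conclusion.** The point holds as a minor one. For two-mode subjects, SAP 4.4 allows a post-selection summary set against an unselected cDBS Baseline, and it leans toward aDBS whenever preference tracks outcome. The questionnaire's own instructions make some tracking plausible.

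With no true benefit, rho = 0.5 and all subjects in two modes, the lean is about 0.12 to 0.20 SD for c between 0.3 and 0.5, with 0.40 SD as the upper bound at that rho. It halves if half the subjects have two modes. The values of f, rho and c are assumptions, so the direction is firmer than the size. If cDBS choosers were left out the lean would grow, but the text leaves their handling open and does not state an exclusion. No primary or secondary conclusion is affected.

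**What to change.** Amend SAP 4.4 and 7.9.3 as follows:

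1. Whenever the selected-mode summary is reported, show beside it, for the same subjects and outcomes, each subject's average over the modes evaluated and the non-selected mode. Label the selected-mode figure as post-selection. The average needs no selection rule, and under the assumptions above its expected inflation is zero.
2. Keep all Evaluation Phase finishers in the denominator. Show subjects who chose cDBS as their own row, and include them in the overall per-subject-average summary.

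PDQ-39, EQ-5D-5L and wearable data from Visits 3 to 6 may be added as support only, with a statement that cDBS choosers are absent and that modes may have been switched.

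The data are already scheduled, so no new visits are needed. The cost is SAP wording, some extra tables and a less favourable figure.

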7.1 Study Subjects

7.1.1 Disposition of Subjects

Subject disposition will be illustrated in a Consolidated Standards of Reporting Trials (CONSORT) diagram and attrition will be identified and summarized. The number of subjects screened, randomized, and receiving therapy will be summarized.

7.1.2 Clinical Investigation Plan (CIP) Deviations

CIP deviations will be listed and the number of deviations will be summarized by type and overall.

